Patients will discontinue Qsymia the week prior to the scheduled operation. The sleeve gastrectomy will be performed by one of the surgeons at the Weight Management Center ([name], [name], [name]) using standard laparoscopic technique. Post-operatively, all patients will be provided with dietary counseling and a nutrition prescription for a very low calorie, high protein diet: 500-700 calories, protein goal of 1-1.2g/kg IBW, and 60-75g carbohydrate. Qsymia will be resumed in the second post-operative week at the initial titration dose and increased to the recommended treatment dose of 7.5/46 mg daily. Patients will have standard post-operative surgical follow up at months 1, 3, 6, 9, 12, 18, and 24. During the post-operative phase, all patients will be enrolled in the bariatric support group program that meets on a monthly basis. Patients will also have at least 3 visits with a clinic dietitian to review and update dietary prescriptions. At any point during this course of follow up, a determination can be made that the primary outcome event has occurred if the patient has a weight plateau—defined as weight gain or < 3 lbs weight loss—for 3 consecutive months, remains above a BMI of 39.9 kg/m² and continues to have associated co-morbidities. These patients will be evaluated for the possibility of moving forward to the next operative stage (laparoscopic Roux-en-Y gastric bypass) while all other patients will continue on with medication and diet/exercise therapy.

Control Group

Control subjects for the proposed study will be identified from the patient population at the Wake Forest Baptist Health Weight Management Center. They will be matched to subjects in the treatment group on age, sex, ethnicity, and BMI. They will be a historical control group who had surgery prior to the commencement of the proposed study (retrospective review).

Trial Design

Prospective independent historical case control

Inclusion Criteria

Inclusion criteria for the proposed study are:

- BMI \geq 50 kg/m²
- Determined to be a good candidate for surgery based on medical and psychological exam.
- Willing to participate in a 3-6 month medically supervised weight loss plan prior to surgery.
- Planning to remain in the reasonable vicinity of the Wake Forest Baptist Health Weight Management Center for the duration of the study.

Exclusion Criteria

- History of prior weight loss surgery (removal/conversion from band to sleeve will not be excluded)

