- Pregnant (women of childbearing potential will complete a pregnancy test (blood draw) to make sure they are not pregnant at the time that they initiate the medication). Ongoing monitoring of pregnancy status is the responsibility of the patient and they are instructed as such in the consent form.
- Ongoing use of weight loss medication
- Contraindications to use of Qsymia, including pregnancy, history of glaucoma, unstable cardiac disease (unstable angina, recent heart attack or stroke (in the past 6 months), uncontrolled arrhythmia), hyperthyroidism, taking MAOIs (monoamine oxidase inhibitors) or allergy to either topiramate or sympathomimetic amines like phentermine.

Patients may be removed from the study at any point if they are unable to tolerate the study medication or are less than 50% compliant with the study medication (take less than 50% of the recommended dose). If a patient is removed from the study due to medication intolerance or non-compliance, the study physician will meet with them and instruct them on how to stop the medication.

Primary endpoint

The primary endpoint for this study is the proportion of patients that meet the criteria to move forward with the second surgical procedure (Roux en Y Gastric Bypass). The criteria include all of the following at any point in the 24 month post-surgical follow up period:

1. Weight plateau (defined as weight gain or < 3 lbs weight loss) for at least 3 months
2. Remains above a BMI of 39.9 kg/m²
3. Continues to have obesity associated co-morbidities (Co-morbidities include hypertension, type 2 diabetes mellitus or pre-diabetes, hyperlipidemia, metabolic syndrome, obstructive sleep apnea, osteoarthritis, non-alcoholic steatohepatitis (NASH), gastroesophageal reflux disease (GERD)).

We hypothesize that the study group treated with Qsymia plus surgery will have a lower rate of occurrence of the primary endpoint at 24 months post-surgery compared to the group with surgery only.

Secondary endpoints

The secondary endpoints for this study are percent weight loss both before and after surgery and changes in percent body fat and resting metabolic rate.

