We hypothesize that the study group treated with Qsymia plus surgery will have greater percent weight loss at all time points compared to the group treated with surgery only. We also hypothesize that the study group treated with Qsymia plus surgery will have a higher resting metabolic rate after adjustment for lean body mass compared to the group treated with surgery only.

Other measures obtained by chart review

Height will be measured at all new patient visits and will be repeated at 24 months to account for any changes over the course of participation. Weight is measured at every clinic visit and will be captured for the study at the time points in the table below. Waist circumference will be measured at the level of the umbilicus at the time points reported in the table. Resting metabolic rate will be measured using expired gas analysis via the MEDGem analyzer. This will be measured following the protocol suggested by the manufacturer, including after refraining from eating, drinking, caffeine or exercise for at least 4 hours prior and immediately following a 10 minute period of quiet rest. Body fat percentage will be measured using Bioelectrical Impedance Analysis via the RJL Systems Quantum II. The Quantum II provides body fat percentage as well as a calculation of total lean mass and total fat mass.

Blood Measures

Blood will be drawn at baseline, 3 months, 6 months, 12 months, 18 months and 24 months and stored for use in later analysis.

Boxes marked with UC are tests that are done as part of usual care. Boxes marked with R are tests done for research only.

Test	BL	1m	3m	6m	9m	12m	18m	24m
Resting Metabolic Rate (MEDGem Analyzer)	UC			R		R		R
Body Fat % by Bioelectrical Impedance Analysis (RJL Systems)	UC			R		R		R
Height	UC							R
Weight	UC	UC	UC	UC	UC	UC	UC	UC
Waist Circumference	UC			R		R		R
Blood draw	R		R	R		R	R	R

Monitoring of Side Effects to study medication

Monitoring for side effects will be performed at each visit. Report of suicidal ideation will lead to study discontinuation and withdrawal from medication. Endpoint will be considered reached in this instance.

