This is an independent case-control study. Analyses will include completers only. Completers are defined as individuals who enter treatment and continue it (Qsymia and/or gastric sleeve) for at least 24 months without reversal or discontinuation. Participants will be recruited until the sample size of 20 cases is obtained. If a participant consents but does not have surgery, this person will not be counted as a case and thus, recruitment will continue.

Data will be entered into and stored in a REDCap database with access given only to individuals who are part of the study team. Study data uploaded will include information from the weekly clinic questionnaire, adverse events, as well as study outcomes (weight at clinic visits), demographic information, etc.

[figure not shown]
Most of the statistical analyses will be conducted using SPSS or SAS. Prior to testing the specific aims, descriptive statistics will be used to characterize the sample. Next, the groups will be compared using the chi-square statistic and T-test statistic to determine whether differences existed between the groups on key variables that may have an effect on outcomes. The case-control matching procedure should insure balance between the treatment groups on sex, age, BMI and ethnicity, but additional analyses will be used to examine the comparability between groups on baseline body composition, waist circumference, and resting metabolic rate.

The primary endpoint for this study is the proportion of patients that meet the criteria to move forward with the second surgical procedure (Roux en Y Gastric Bypass) at any point during follow up. The proportion of the Qsymia treated group that achieves the primary endpoint will be compared to the surgery only group after 24 months of follow up. Unadjusted and adjusted models will be developed to test for differences in the rate of the primary endpoint occurrence by treatment group.

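### Completers are the only efficacy analysis set: membership is decided during the 24 months in which the endpoint is counted, through exits that only Qsymia patients can take, and the definition is unclear

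*Combined protocol and SAP*

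**What the plan says.** All references are to the combined protocol and SAP.

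- **Statistical analysis:** "Analyses will include completers only. Completers are defined as individuals who enter treatment and continue it (Qsymia and/or gastric sleeve", and must do so "for at least 24 months without reversal or discontinuation". No other efficacy set and no sensitivity analysis for this choice is planned.
- **Primary endpoint:** a patient counts as an event when three criteria (weight plateau, BMI above 39.9, continuing co-morbidity) are met. "The criteria include all of the following at any point in the 24 month post-surgical follow up period".
- **Exclusion Criteria, removal rule:** "Patients may be removed from the study at any point if they are unable to tolerate the study medication", or if they take under half of the recommended dose.
- **Monitoring of Side Effects to study medication:** suicidal ideation leads to discontinuation from the study and from the drug, and "Endpoint will be considered reached in this instance". A heart rate above 100 at two consecutive visits leads to withdrawal from the drug, with similar wording about the endpoint.
- **Control Group:** "They will be a historical control group who had surgery prior to the commencement of the proposed study (retrospective review".
- **Treatment Group:** Qsymia is stopped in the week before the operation and restarted in the second week after it. Of patients who meet the endpoint, the plan says "These patients will be evaluated for the possibility of moving forward to the next operative stage", "while all other patients will continue on with medication and diet/exercise therapy".
- **Safety Monitoring:** adverse-event and blood-chemistry reporting is not limited to completers. The point here concerns efficacy only.

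**The concern.** A patient's place in the analysis depends on what happens after surgery, during the same period in which the endpoint can occur. The listed exits are tied to taking or tolerating Qsymia, so a surgery-only control cannot leave by them. Matching on age, sex, ethnicity and BMI balances the groups at entry and does nothing about selection afterwards.

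If patients who leave have a different endpoint rate from those who stay, the Qsymia rate among completers differs from the rate among all operated Qsymia patients, and the control rate has no matching shift. The primary comparison is then biased: toward Qsymia if events are lost more often than non-events, against it in the reverse case.

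The set also cannot be built with confidence from the text:

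- The and/or wording does not say whether a patient who stops the drug but keeps the sleeve is a completer.
- The start of the 24 months is not given, although at least 3 months of medical therapy precede surgery.
- The planned stop before the operation conflicts literally with the requirement of no discontinuation.

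With about 20 patients per group, a few patients moved in or out can change the conclusion.

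**Working it through.** **Inputs.** Control rate 0.70, Qsymia rate 0.25, alpha 0.05, uncorrected chi-square, stated power .840 (Sample size justification); 20 cases (Statistical analysis). The test is taken as two-sided. The documents give no loss fractions; all those below are assumptions.

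**The plan's own figure.** Normal approximation with pooled variance under the null, 20 v 20:

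- Mean rate = (0.70 + 0.25)/2 = 0.475
- SE under the null = √(0.475 × 0.525 × 2/20) = 0.1579
- SE under the alternative = √(0.70 × 0.30/20 + 0.25 × 0.75/20) = 0.1410
- Power = Φ((0.45 − 1.96 × 0.1579)/0.1410) = Φ(0.997) = 0.8405

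This matches .840 at 20 v 20. At the 25 v 20 named in the same section the formula gives 0.880. That mismatch is a separate matter; the main results are checked at both sizes. Exact enumeration of the chi-square at 20 v 20 gives power 0.823.

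**Selection among completers.** Let the true rate be p, and let fractions a of events and b of non-events be lost, from the Qsymia group only. The rate among those kept is

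r = p(1 − a) / [p(1 − a) + (1 − p)(1 − b)].

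With no drug effect (p = 0.70 in both groups):

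- a = b: r = 0.70, unchanged.
- a = 30%, b = 10%: 0.49/(0.49 + 0.27) = 0.645.
- a = 50%, b = 30%: 0.35/(0.35 + 0.21) = 0.625.
- a = 10%, b = 30%: 0.63/(0.63 + 0.21) = 0.750.

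**Chance of a significant result favouring Qsymia.** This sums the binomial probabilities of every table in which the uncorrected chi-square has p < 0.05 and the Qsymia rate is lower. Each of 20 Qsymia patients is a kept event, a kept non-event or excluded; all 20 controls are kept. The third column refills the Qsymia group to 20 completers.

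| Loss of events / non-events | Not replaced | Replaced to 20 |
|---|---|---|
| none | 0.0266 | 0.0266 |
| 10% / 10% | 0.0263 | 0.0266 |
| 20% / 20% | 0.0270 | 0.0266 |
| 30% / 30% | 0.0284 | 0.0266 |
| 30% / 10% | 0.0569 | 0.0587 |
| 50% / 30% | 0.0702 | 0.0749 |
| 10% / 30% | 0.0119 | 0.0110 |

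With 25 Qsymia patients and no replacement, the results for none, 20/20, 30/10, 50/30 and 10/30 are 0.0249, 0.0255, 0.0561, 0.0719 and 0.0105.

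**Both tails.** In the 30/10 case the tail against Qsymia is 0.0106, so total two-sided error is 0.0569 + 0.0106 = 0.0675. With no loss it is 2 × 0.0266 = 0.053.

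**Effect of the and/or wording (invented counts).** Suppose 7/20 Qsymia v 14/20 controls, where four Qsymia patients stopped the drug but kept the sleeve. Using χ² = N(ad − bc)²/(product of the four margins):

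- All four counted as completers: 40 × (7 × 6 − 13 × 14)²/(20 × 20 × 21 × 19) = 4.91, p = 0.027.
- All four dropped, none had the event (7/16): χ² = 2.52, p = 0.112.
- All four dropped, all had the event (3/16): χ² = 9.37, p = 0.002.

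**The case against.** The strongest reply is that the and/or wording may keep sleeve patients who stopped the drug, in which case much of the drug-related exclusion goes away. This stands in part: the ambiguity and the one-sided exclusion do not both apply at full strength. But the text does not choose that reading, and the removal rule under Exclusion Criteria still takes intolerant or non-compliant patients out of the study, so their outcomes may never be recorded.

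A second reply is that every loss fraction is assumed, and that the two-sided error in the 30/10 case (6.75%) is a modest rise on 5.3% in a declared pilot. That is a fair statement of size. The plan nevertheless sets a hypothesis test with alpha and power for the primary endpoint, and invokes the pilot design only to forgo multiplicity adjustment of secondary outcomes.

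Three stronger readings are tempting, and the documents do not support them:

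- *Patients are dropped for having the endpoint.* Saying that the others continue medication might suggest that patients evaluated for bypass stop it, or that conversion is a discontinuation. If so, they would be excluded because of their outcome. The text says neither, and evaluation is only for the possibility of bypass. For scale only: losing 30% of Qsymia events and no non-events would give 7.5%.
- *Safety withdrawals are scored as second-surgery events.* The endpoint-reached wording could equally mean end of participation. Only the first meaning conflicts with the Primary endpoint and Statistical analysis sections.
- *The planned pre-operative stop excludes every operated Qsymia patient.* That follows only from a literal reading; the plan restarts the drug, so it is a wording conflict to reconcile.

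**Conclusion.** The concern holds for the efficacy analyses. The plan states a rule, with no alternative analysis, that selects patients on post-surgical events inside the endpoint window, through exits open to one group only. No other section repairs this.

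Whether bias results depends on whether loss is related to outcome. If it is not, the chance of a false result favouring Qsymia stays near 2.7%. If events are lost more often, it rises, for example to 5.7% at 30/10; in the reverse case it falls to 1.2%. Recruiting replacements does not remove this. These figures assume a true rate of 70% in both groups, 20 v 20, and loss fractions not found in the documents. A reader might infer that the plan favours Qsymia; the documents fix neither direction nor size.

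Separately, the completer definition is too unclear to fix the analysis set. This needs correcting before analysis, and outcome follow-up needs correcting sooner, since outcomes not collected after removal may not be recoverable.

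**What to change.** 1. Make the primary efficacy set every Qsymia participant who has the sleeve gastrectomy and every matched control. Select controls without regard to completion of 24 months or to outcome; picking only charts with full follow-up would be selection too.
2. Score the three endpoint criteria through month 24 regardless of drug discontinuation, adherence or conversion. Count criteria met before conversion as an event in both groups.
3. Keep recording weight and co-morbidity status for participants removed under the Exclusion Criteria rule or withdrawn under Monitoring of Side Effects.
4. Pre-specify one primary handling of unknown month-24 status. Bound the result by opposite assignments: Qsymia unknowns as events with control unknowns as non-events, then the reverse. Giving both groups the same assignment does not bound the comparison.
5. Keep completers as a supportive analysis, with the and/or wording, the start of the 24 months, reversal, discontinuation and the planned pre-operative stop all defined.
6. Reconcile the endpoint-reached wording with the Primary endpoint and Statistical analysis sections before analysis. If it means end of participation, do not add a sensitivity analysis that counts drug-safety withdrawals as second-surgery events.
7. Report the number of, and reasons for, Qsymia participants who stop before surgery. They stay outside this set, which is a limitation.

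**Cost.** SAP wording, plus a protocol change so that outcome follow-up continues after removal or study discontinuation. Weight is already usual care at every scheduled time point; co-morbidity status is not in the schedule of tests, so some extra follow-up and chart abstraction is needed in both groups.

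The effect may be diluted. If completers have rate 0.25 and stoppers 0.70, 10% stopping gives 0.9 × 0.25 + 0.1 × 0.70 = 0.295, and 20% gives 0.8 × 0.25 + 0.2 × 0.70 = 0.340. Power at 20 v 20 (the normal approximation above) is then 0.745 and 0.634, against 0.841 with no stopping. These stopping fractions are also assumptions.

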At each physician visit (monthly during phase one and at months 1, 3, 6, 9, 12, 15, 18, and 24 during phase 2) the participant will complete an adverse events questionnaire in addition to the signs and symptoms clinic questionnaire. All adverse events will be reviewed by the study coordinator to clarify any details or questions about the reported event. The PI will then review each adverse event and determine the likelihood that the event was related to the study and whether or not it was an expected event. Study clinicians will also review the medical record at clinic visits to determine if any event or medical care occurring in the interim was related to safety and/or side effects. Any event requiring immediate reporting will be reported as such. All adverse event data will be recorded in RedCAP and tabulated every 6 months for cumulative review. The PI will be responsible for reporting cumulative frequencies of adverse events for those on study drug. Additionally, any derangements in blood

chemistries that are being monitored as part of this study will be cataloged, and frequencies will be reported for all study participants every 6 months.

Participants will be asked to bring in their pill bottles to count any remaining pills at each visit. Missed doses of medication will be noted and any excess medication will be discarded at the refill visits in the hazardous waste containers per clinic protocol. Participants will be provided with only the medication required to provide daily doses until the next scheduled clinic visit.

Some patients enrolled in the study may have diabetes and be on hypoglycemic medications or insulin prior to surgery. As part of usual care, individuals with diabetes are instructed to reduce all diabetes medication by 50% before leaving the hospital after weight loss surgery and are instructed to follow-up with their primary care provider 2 weeks after surgery in order to monitor or modify medications for diabetes and other comorbid conditions such as blood pressure. In addition, discharge documents are sent to each patient's primary care provider either through Wake One or in paper form. Prior to surgery, patients are expected to develop a relationship with a primary care provider.

Statistical analysis

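### The primary denominator is defined by continuing treatment, not by having the weights needed to score the endpoint, and no rule covers completers whose outcome was not observed

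*Combined protocol and SAP*

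**What the plan says.** **Denominator.** The Statistical analysis section states "Analyses will include completers only" and then "Completers are defined as individuals who enter treatment and continue it (Qsymia and/or gastric sleeve) for at least 24 months without reversal or discontinuation". The definition mentions no visit, weight or chart entry.

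**Numerator.** The same section says "The primary endpoint for this study is the proportion of patients that meet the criteria to move forward with the second surgical procedure". The Primary endpoint section adds "The criteria include all of the following at any point in the 24 month post-surgical follow up period". The first criterion is "Weight plateau (defined as weight gain or < 3 lbs weight loss) for at least 3 months"; the other two are BMI still above 39.9 kg/m² and continuing co-morbidity.

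**Timing.** The Statistical analysis section says "The proportion of the Qsymia treated group that achieves the primary endpoint will be compared to the surgery only group after 24 months of follow"-up.

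**Source of data.** On controls, the Control Group section says: "They will be a historical control group who had surgery prior to the commencement of the proposed study (retrospective review". For the Qsymia group, the Safety Monitoring section says: "Participants will be provided with only the medication required to provide daily doses until the next scheduled clinic visit".

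No section says how a completer with missing weights is classified. None sets a minimum amount of follow-up data for a control.

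**The concern.** Numerator and denominator rest on different facts. A failure needs positive evidence: weights at least three months apart, a BMI and co-morbidity status. Staying in the denominator needs only that treatment was not reversed or stopped. A control's only study-relevant treatment is the sleeve, which normally remains in place whether or not the patient returns to clinic. A control last weighed at month 6 or 12 can therefore satisfy the completer wording and yet never show a later plateau. An event documented before the patient left would still count.

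The groups may be affected unequally. Drug is dispensed only up to the next visit, so a patient who must stay on Qsymia for 24 months to be a completer must keep attending and will be weighed. Controls are seen only as often as routine care brought them in. If so, the control failure proportion is pulled down and the treated one is not. A null result in this pilot could then reflect thin chart follow-up in controls and not absence of effect.

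**Working it through.** **Inputs from the documents (Sample size justification):** control failure 0.70 (called approximate), experimental failure 0.25, uncorrected chi-square, type I error 0.05 (taken as two-sided), 25 experimental and 20 control subjects, power 0.840. The Statistical analysis section gives 20 cases.

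**The plan's own figure.** Power = Φ[(|pC − pT| − 1.96·s0)/s1], where s0 = √[p̄(1 − p̄)(1/nC + 1/nT)] and s1 = √[pC(1 − pC)/nC + pT(1 − pT)/nT].

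- 20 v 20: p̄ = 0.475, s0 = 0.1579, s1 = 0.1410; (0.45 − 0.3095)/0.1410 = 0.996; power 0.840 (exact enumeration 0.823).
- 25 v 20: p̄ = 0.450, s0 = 0.1492, s1 = 0.1342; (0.45 − 0.2925)/0.1342 = 1.174; power 0.880 (exact 0.874).

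The stated 0.840 is therefore the 20-per-group figure. Both sizes are carried below.

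**Assumptions not in the documents.** First documentable events fall at months 6/9/12/18/24 in shares 5/10/20/45/20%. This is only loosely guided by the 12-18 month plateau mentioned in the rationale. Dropout is permanent and unrelated to outcome. Attendance at those five visits is:

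- A: 95/90/85/80/75%
- B: 90/85/80/70/60%
- C: 85/75/70/55/40%

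**Observed control rate** = 0.70 × f, where f = Σ(event share × attendance).

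- A: f = 0.0475 + 0.09 + 0.17 + 0.36 + 0.15 = 0.8175; rate 0.572 (−18%)
- B: f = 0.045 + 0.085 + 0.16 + 0.315 + 0.12 = 0.725; rate 0.508 (−28%)
- C: f = 0.0425 + 0.075 + 0.14 + 0.2475 + 0.08 = 0.585; rate 0.410 (−42%)

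**Power, unobserved patients left in as event-free.**

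| Month-24 attendance | Loss in controls only, 20 v 20 | Loss in controls only, 25 v 20 | Same loss in both groups, 20 v 20 |
|---|---|---|---|
| 100% | 0.84 | 0.88 | 0.84 |
| A: 75% | 0.55 | 0.60 | 0.68 (0.57 v 0.20) |
| B: 60% | 0.39 | 0.43 | 0.59 (0.51 v 0.18) |
| C: 40% | 0.18 | 0.21 | 0.46 (0.41 v 0.15) |

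For B at 20 v 20, controls only: p̄ = 0.379, s0 = 0.1534, s1 = 0.1479; (0.2575 − 0.3007)/0.1479 = −0.292; power 0.385.

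**A simpler model as a check.** Let 10/20/30% of controls have no usable weights at all. Left in as event-free, the control rate is 0.70 × (1 − m) = 0.63/0.56/0.49 and power at 20 v 20 is 0.69/0.52/0.34. With only evaluable controls (18/16/14 of 20), the expected rate stays 0.70 and power is 0.82/0.79/0.76.

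**Width of the bounds.** The undetermined share of controls is 1 − observed rate − 0.30 × month-24 attendance. For B this is 1 − 0.5075 − 0.18 = 0.3125, so the control rate lies between 0.51 and 0.82.

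**The case against.** A reader might infer that the plan counts a lost control as a success. The documents do not say that; they are silent on missing outcomes. Two readings would remove such a control. Twenty-four months without reversal cannot be confirmed for a patient last charted at month 6, and a comparison made after 24 months of follow-up may presuppose that the follow-up exists. Controls are also picked retrospectively, so the team could simply choose patients with full charts. This stands as a limit on the claim. It does not close the gap: none of these choices is written down, the follow-up phrase times the comparison and sets no condition of inclusion, and the decision would be made on charts where outcomes are already visible.

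A reader might also infer that ascertainment is complete in the Qsymia group. That depends on the and/or in the completer definition. If the sleeve alone suffices, a treated patient who stops attending and runs out of drug is also a completer, also unobserved, and the asymmetry shrinks. The objection stands, and the controls-only power figures are therefore the worst case.

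The magnitudes rest on assumed attendance and event timing. A control who misses visits but is weighed again at month 24 might still be captured. At assumed 60% attendance a simulated life-table estimate returns 0.70 against a crude 0.51, but only because dropout was simulated as unrelated to outcome. Finally, the bias runs against the hypothesis in a self-described pilot, so it does not favour Qsymia. It can still hide an effect the pilot was set up to look for.

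**Conclusion.** The concern holds in this form: the denominator is set by treatment persistence, the event needs observed weights, and nothing says what happens to a completer without them. Under the literal rule such a patient is event-free by default after the last weight, which biases the control proportion down.

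The size is conditional. With month-24 attendance of 75/60/40% in controls only, 0.70 becomes 0.57/0.51/0.41. Power becomes 0.55/0.39/0.18 at 20 v 20 or 0.60/0.43/0.21 at 25 v 20. With equal attendance in both groups, power at 20 v 20 is about 0.68/0.59/0.46. All of this assumes the stated event timing, permanent dropout unrelated to outcome, and true rates of 0.70 and 0.25. The documents support the structural gap and the direction of bias. They do not support any one of these figures as the expected loss, or a claim that the bias must be confined to controls.

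**What to change.** 1. State whether a treated patient who stops Qsymia but keeps the sleeve is a completer.
2. Apply one evaluability rule to both groups, naming the weights and co-morbidity data needed to score the endpoint. Do not score anyone as event-free after the last recorded post-operative weight.
3. Then choose one analysis in advance:
   - Restrict the chi-square to patients with an event or with weights through month 24. This is simple, but it leans upward, because an early event is kept whatever the later attendance while a non-event needs full follow-up. Under pattern B the control rate would be 0.5075/(0.5075 + 0.18) = 0.74.
   - Estimate the 24-month cumulative proportion by life table on the scheduled visits, censoring at the last weight, and compare the groups at 24 months. This avoids that lean if censoring is unrelated to outcome.
4. Report the number evaluable by group. Repeat the comparison with undetermined patients counted all as non-events and then all as events.
5. Reconcile 25 experimental subjects with 20 cases in the power statement.

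The cost is analysis wording and some programming, with no new visits or patients. Intervals will be wider, and the main estimate assumes that missing follow-up is unrelated to outcome. The bounds probe that assumption, and with poor attendance they will be wide.
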